#### 2) Type of Participant and Target Disease Characteristics

- a) Eastern Cooperative Oncology Group (ECOG) performance status (PS) 0-1 (see [Appendix 6](#))
- b) Life expectancy  $\geq$  6 months

#### 3) Pathologically demonstrated BCG-unresponsive\*, carcinoma in situ (CIS)-containing high-risk NMIBC defined as CIS with or without papillary component required within

**10 weeks (70 days) prior to randomization and must be confirmed by the Pathology Review Committee (PRC).**

\* BCG-unresponsive disease is defined as being at least one of the following:

- Persistent or recurrent CIS alone or with recurrent Ta/T1 (noninvasive papillary disease/tumor invades the subepithelial connective tissue) disease within 12 months of completion of adequate BCG therapy\*\*
- Recurrent high-grade Ta/any T1 disease within 6 months of completion of adequate BCG therapy\*\* [per revised protocol 03, participants must also have CIS to be eligible]
- T1 high-grade disease at the first evaluation following an induction BCG course (at least 5 of 6 induction doses) [per revised protocol 03, participants must also have CIS to be eligible]

\*\* Adequate BCG treatment is defined as at least 2 courses of BCG. This can include 2 induction courses (at least five of six doses of an initial induction course plus at least two of six doses of a second induction course) or 1 induction course (at least 5 of 6 induction doses) and at least 2 of 3 doses of a maintenance cycle (“5+2”).

- a) Predominant histologic component (> 50%) must be urothelial (transitional cell) carcinoma
- b) Must have undergone each of the following procedures within 10 weeks (70 days) of randomization (except 90 days for CT or MRI). If these procedures are performed as part of the participant’s routine care, they do not need to be repeated provided that they were performed within the required time period:
  - i) Complete excision of all papillary disease (T1/TaHG). For participants with T1 lesions, a re-staging TURBT must be performed within 8 weeks after the initial TURBT to ensure that the pathology specimen contains muscularis propria that is free of invasive tumor per PRC.
  - ii) Resection or fulguration of all detectable CIS, if feasible. Fluorescence-guided cystoscopy is encouraged but not mandated. It is understood that due to the nature of this disease, complete resection of CIS cannot be assured.
  - iii) The presence of any suspicious lesions must be recorded and these lesions will be biopsied. Random sampling of bladder mucosa for detection of occult CIS during the screening period is optional, but should be performed at the time of screening transurethral resection/biopsy of bladder tumor and/or CIS within 10 weeks (70 days) of randomization, if possible. The bladder should be mapped by visual inspection and random biopsies taken from the trigone, right and left lateral walls, posterior wall, dome and prostatic urethra (in male participants).
  - iv) Urine cytology must be obtained from a voided specimen (except from the first morning urination) or by bladder wash. Recognizing the possibility of occult CIS, cytology at screening does not need to be negative for study participation.
  - v) Computed tomography (CT) scan of the chest and CT or magnetic resonance imaging (MRI) of the abdomen, pelvis, and all other areas of suspected disease to exclude

- locally advanced or metastatic bladder cancer or synchronous UC in the upper urinary tracts within 90 days prior to randomization.
- vi) Participants should either be deemed medically unfit for radical cystectomy, or should have refused radical cystectomy after consultation with their urologist or oncologist.
  - vii) If tumor tissue was obtained > 70 days prior to randomization, participants must have a repeat cystoscopy  $\leq$  70 days prior to randomization (see [Section 9.1.4](#)).
  - c) Pelvic examination, preferably under anesthesia, should be performed within 10 weeks (70 days) of randomization to exclude locally advanced disease.
  - d) Availability of a suitable formulation and mode of administration of BMS-986205 for the participant's needs, as detailed in the IB and pharmacy manual at the time of enrollment. Please contact the Medical Monitor with any queries.

#### 4) Age and Reproductive Status

- a) Males and Females, 18 years of age, or age of majority, and older
- b) Women of childbearing potential (WOCBP) must have a negative serum or urine pregnancy test (minimum sensitivity 25 IU/L or equivalent units of HCG) within 24 hours prior to the start of study treatment.
- c) Women must not be breastfeeding
- d) Women of childbearing potential (WOCBP) must agree to follow instructions for method(s) of contraception (see [Appendix 4](#)) for the duration of treatment with study treatment plus 5 months after the last dose of study treatment (ie, 30 days [duration of ovulatory cycle] plus the time required for nivolumab to undergo approximately 5 half-lives).
- e) Males who are sexually active with WOCBP must agree to follow instructions for method(s) of contraception (see [Appendix 4](#)) for the duration of treatment with study treatment plus 1 month (approximately 4 weeks) after the last dose of the study treatment. In addition, male participants must be willing to refrain from sperm donation during this time.
- f) Male participants will be required to always use a latex or other synthetic condom during any sexual activity (eg, vaginal, anal, oral) with WOCBP; even if the participants have undergone a successful vasectomy or if their partner is already pregnant or breastfeeding. Males should continue to use a condom while on study plus 1 month (approximately 4 weeks) after the last dose of the study treatment. This criterion applies to azoospermic males as well.
- g) WOCBP who are continuously not heterosexually active are exempt from contraceptive requirements, and still must undergo pregnancy testing as described in this section.

Investigators shall counsel WOCBP, and male participants who are sexually active with WOCBP, on the importance of pregnancy prevention and the implications of an unexpected pregnancy. Investigators shall advise on the use of highly effective methods of contraception ([Appendix 4](#)), which have a failure rate of < 1% when used consistently and correctly. **Hormonal contraceptives are not highly effective methods of contraception for participants in Arms C and D of this study who are WOCBP treated with BMS-986205, since drug interactions of BMS-986205 with hormone-based contraceptives are not yet known.**

## 6.2 Exclusion Criteria

### 1) Medical Conditions

- a) Women who are pregnant or breastfeeding
- b) Participants with an active, known or suspected autoimmune disease. Participants with type I diabetes mellitus, hypothyroidism only requiring hormone replacement, skin disorders (such as vitiligo, psoriasis, or alopecia) not requiring systemic treatment, or conditions not expected to recur in the absence of an external trigger are permitted to enroll.
- c) Prior malignancy active within the previous 3 years except for locally curable cancers that have been apparently cured, such as basal or squamous cell skin cancer, prostate cancer with evidence of undetectable Prostate Specific Antigen (PSA), or carcinoma in situ of the cervix or breast
- d) Participants with serious or uncontrolled medical disorders
- e) Participants with a personal or family (ie, in a first-degree relative) history of cytochrome b5 reductase deficiency (previously called methemoglobin reductase deficiency) or other diseases that put them at risk of methemoglobinemia. All participants will be screened for methemoglobin levels prior to randomization.
- f) Participants with a history of G6PD deficiency or other congenital or autoimmune hemolytic disorders. All participants will be screened for G6PD deficiency prior to randomization.
- g) Evidence of locally advanced disease or metastatic bladder cancer as seen in cross-sectional images of the chest, abdomen, and pelvis
- h) Urothelial cancer (UC) in the upper genitourinary tract (kidneys, renal collecting systems, ureters) within 24 months of enrollment
- i) UC and/or CIS in the prostatic urethra within 12 months of enrollment
- j) Locally advanced disease demonstrated by pelvic examination preferably performed under anesthesia
- k) Previous or concurrent muscle invasive or disseminated/metastatic bladder cancer
- l) Participants must have recovered from the effects of major surgery requiring general anesthetic or significant traumatic injury at least 14 days before treatment assignment.
- m) Uncontrolled adrenal insufficiency
- n) New York Heart Association (NYHA) functional Classification of Heart Failure: Class III or Class IV
- o) All toxicities attributed to prior anti-cancer therapy other than alopecia and fatigue must have resolved to Grade 1 (NCI CTCAE version 4) or baseline before administration of study drug. Participants with toxicities attributed to prior anti-cancer therapy which are not expected to resolve and result in long lasting sequelae, such as peripheral neuropathy after platinum based therapy, are permitted to enroll.
- p) Dementia, altered mental status, or any psychiatric condition that would prohibit the understanding or rendering of informed consent or completing quality of life questionnaire.
- q) Uncontrolled intercurrent illness including, but not limited to, ongoing or active infection, unstable angina pectoris, or psychiatric illness/social situations that would limit compliance with study requirements.

- r) Participants with interstitial lung disease that is symptomatic or may interfere with the detection or management of suspected drug-related pulmonary toxicity.
- s) Participants with active interstitial lung disease / pneumonitis or with a history of interstitial lung disease/ pneumonitis requiring steroids
- t) Prior history of serotonin syndrome

## 2) Prior/Concomitant Therapy

- a) Participants with a condition requiring systemic treatment with either corticosteroids (> 10 mg daily prednisone equivalent) or other immunosuppressive medications within 14 days of start of study treatment. Inhaled or topical steroids, and adrenal replacement steroid doses > 10 mg daily prednisone equivalent, are permitted in the absence of active autoimmune disease.
- b) Prior treatment with an anti-PD-1, anti-PD-L1, anti-PD-L2, or anti-CTLA-4 antibody, or any other antibody or drug specifically targeting T-cell co-stimulation or checkpoint pathways
- c) Prior treatment with BMS-986205 or any other IDO1 inhibitors
- d) Treatment with botanical preparations (eg, herbal supplements or traditional Chinese medicines) intended for general health support or to treat the disease under study within 2 weeks prior to randomization
- e) Prior systemic chemotherapy or immunotherapy for UC. Intravesical chemotherapy and/or interferon administered prior to the date of tumor sample submission is permitted.
- f) Prior radiation therapy for bladder cancer
- g) Prior surgery for bladder cancer other than TURBT and/or bladder biopsies
- h) Use of an investigational agent within 4 weeks of randomization.
- i) Participants who have received a live /attenuated vaccine within 30 days of first treatment.

## 3) Physical and Laboratory Test Findings

- a) WBC < 2000/ $\mu$ L
- b) Neutrophils < 1500/ $\mu$ L
- c) Platelets < 100\* 10^3/ $\mu$ L
- d) Hemoglobin < 9.0 g/dL (transfusion to achieve this level is not permitted within 2 weeks of this laboratory assessment)
- e) Serum creatinine > 1.5x ULN, unless creatinine clearance (CLcr)  $\geq$  40 mL/min (measured or calculated using the Cockcroft-Gault formula):  
Female CLcr =  $\frac{(140 - \text{age in years}) \times \text{weight in kg} \times 0.85}{72 \times \text{serum creatinine in mg/dL}}$   
Male CLcr =  $\frac{(140 - \text{age in years}) \times \text{weight in kg} \times 1.00}{72 \times \text{serum creatinine in mg/dL}}$
- f) AST or ALT > 3.0x ULN
- g) Total bilirubin > 1.5x ULN (except participants with Gilbert Syndrome who must have a total bilirubin level of < 3.0x ULN)

- h) Any positive test result for hepatitis B virus or hepatitis C virus indicating presence of virus, eg, Hepatitis B surface antigen (HBsAg, Australia antigen) positive, or Hepatitis C antibody (anti-HCV) positive (except if HCV-RNA negative)
- i) Known history of positive test for human immunodeficiency virus (HIV) or known acquired immunodeficiency syndrome (AIDS). Note: Testing for HIV must be performed at sites where mandated locally. See [Appendix 11](#).
- j) Quantitative or qualitative G6PD assay results suggesting underlying G6PD deficiency
- k) Blood methemoglobin > ULN, assessed in an arterial or venous blood sample or by co-oximetry
- l) Positive pregnancy test at enrollment or prior to administration of study medication

#### **4) Allergies and Adverse Drug Reaction**

- a) History or presence of hypersensitivity or idiosyncratic reaction to methylene blue
- b) History of allergy or hypersensitivity to study drug components

#### **5) Other Exclusion Criteria**

- a) Prisoners or participants who are involuntarily incarcerated. (Note: under specific circumstances and only in countries where local regulations permit a person who has been imprisoned may be included as a participant. Strict conditions apply and BMS approval is required.)
- b) Participants who are compulsorily detained for treatment of either a psychiatric or physical (eg, infectious disease) illness

Eligibility criteria for this study have been carefully considered to ensure the safety of the study participants and that the results of the study can be used. It is imperative that participants fully meet all eligibility criteria.

### **6.3 Lifestyle Restrictions**

Not applicable. No restrictions are required.

### **6.4 Screen Failures**

Screen failures are defined as participants who consent to participate in the clinical study, may be randomized, but are not subsequently treated. A minimal set of screen failure information is required to ensure transparent reporting of screen failure participants, to meet the Consolidated Standards of Reporting Trials (CONSORT) publishing requirements, and to respond to queries from regulatory authorities. Minimal information includes date of consent, demography, screen failure details, eligibility criteria, and any serious AEs.

#### **6.4.1 Retesting During Screening or Lead-In Period**

**Participant Re-enrollment:** This study permits the re-enrollment of a participant that has discontinued the study as a pre-treatment failure (ie, participant has not been treated). If re-enrolled, the participant must be re-consented.

Retesting of laboratory parameters and/or other assessments within any single screening or lead-in period will be permitted (in addition to any parameters that require a confirmatory value).

The most current result prior to randomization is the value by which study inclusion will be assessed, as it represents the participant's most current, clinical state.

Laboratory parameters and/or assessments that are included in [Table 2-1](#), Screening Procedural Outline, may be repeated in an effort to find all possible well-qualified participants. Consultation with the Medical Monitor may be needed to identify whether repeat testing of any particular parameter is clinically relevant.

## **7 TREATMENT**

Study treatment is defined as any investigational treatment(s), marketed product(s), placebo or medical device intended to be administered to a study participant according to the study randomization or treatment allocation.

An investigational product (IP), also known as investigational medicinal product (IMP) in some regions, is defined as a pharmaceutical form of an active substance or placebo being tested or used as a reference in a clinical study, including products already with a marketing authorization but used or assembled (formulated or packaged) differently than the authorized form, or used for an unauthorized indication, or when used to gain further information about the authorized form.

Nivolumab, BMS-986205, and BCG are IPs/IMPs in this study ([Table 7-1](#)).

Other medications used as support or escape medication for preventative, diagnostic, or therapeutic reasons, as components of the SOC for a given diagnosis, may be considered as non-IPs.

**Table 7-1: Study Treatments for CA2099UT**

Product Description / Class and Dosage Form	Potency	IP/Non-IP	Blinded or Open Label	Packaging / Appearance	Storage Conditions (per label)
BMS-936558-01 (Nivolumab) Solution for Injection a	10 mg/mL	IP	Open Label	Vial	Refer to the label on container and/or pharmacy manual
BMS-986205-04	50 mg or 100 mg	IP	Open Label	Tablet	Refer to the label on container and/or pharmacy manual
BCG b	Dose according to prescribing information for BCG strain and preparation administered	IP	Open Label	Vial	Refer to the label on container and/or pharmacy manual

a May be labeled as “Nivolumab” or “BMS-936558-01 Solution for Injection.”

b These products may be obtained by the investigational sites as local commercial product in certain countries if allowed by local regulations. These products should be prepared/stored/administered in accordance with the package insert or summary of product characteristics (SmPC).

## 7.1 Treatments Administered

The selection and timing of dose for each participant is presented in Table 7.1-1.

Study treatment will be dispensed at the study visits as listed in the Schedule of Activities (Section 2).

**Table 7.1-1: Selection and Timing of Dose**

Study Treatment	Unit dose strength(s)/Dosage level(s)	Dosage formulation Frequency of Administration	Route of Administration
Nivolumab	480 mg	Solution for injection/ every 4 weeks	IV
BMS-986205	100 mg	Tablet/once daily	PO
BMS-986205	50 mg	Tablet/once daily	PO
BCG	Dose according to prescribing information for BCG strain and preparation administered	Once weekly for 6 weeks, followed by once weekly for 3 weeks at 3 months, 6 months, and 12 months after first BCG dose	intravesical

### 7.1.1 Nivolumab Dosing

Participants should receive nivolumab at a dose of 480 mg as a 30-minute infusion on Day 1 of each treatment cycle (1 cycle = 4 weeks) until recurrence, progression, unacceptable toxicity, withdrawal of consent, or completion of 52 weeks of treatment, whichever occurs first. Participants randomized to Arms A or C should begin study treatment within 3 calendar days of randomization. Participants randomized to Arms B or D should begin study treatment within 3 calendar days of randomization or after 14 days from last TURBT or bladder biopsy, whichever is later.

No dose escalations or reductions are allowed for nivolumab after the safe-dose level has been determined in the safety lead-in. For Q4W dosing cycles, participants may be dosed within a  $\pm 3$  day window. Premedication is not recommended for the first dose of nivolumab.

Participants should be carefully monitored for infusion reactions during nivolumab administration. If an acute infusion reaction is noted, participants should be managed according to Section 7.7.5.

Doses of nivolumab may be interrupted (ie, infusion interruption), delayed, or discontinued depending on how well the participant tolerates the treatment. Dosing visits are not skipped, only delayed. BMS-986205 treatment should be continued if nivolumab dosing is interrupted or delayed. BMS-986205 treatment should be discontinued if nivolumab administration is discontinued.

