### **5.5.2 Justification for BMS-986205 Dose**

All participants will receive BMS-986205 100 mg PO QD in combination with nivolumab 480 mg Q4W. The selection of the dose and schedule for BMS-986205 is primarily based on available data from the ongoing Phase 1/2, first-in-human Study CA017003.

In Study CA017003, doses of BMS-986205 from 25 mg to 400 mg QD in combination with nivolumab were studied in the dose escalation part and doses of BMS-986205 100 mg and 200 mg QD were evaluated in selected expansion cohorts. The maximum tolerated dose of BMS-986205 established in this study was 200 mg QD.

At 100 mg, preliminary PK data indicated that average trough plasma levels of BMS-986205 exceeded the in vitro human whole blood IC90. Significant and sustained inhibition of serum kynurenine levels was observed at all dose levels. PK-pharmacodynamic analysis of BMS-986205 exposure and kynurenine inhibition further suggests the effects to plateau at doses starting at 100 mg QD. Maximum inhibition of serum kynurenine levels were predicted to be similar at 100 mg QD (61%) and 200 mg QD (64%). Marked but variable inhibition of intratumoral kynurenine levels was also observed at both dose levels.

Preliminary safety data (as of 11-Oct-2017) from Study CA017003 indicate that BMS-986205 is safe and tolerable at both 100 mg QD and 200 mg QD. The data suggest a more favorable tolerability profile at 100 mg, with fewer participants experiencing treatment-related  $\geq$  Grade 3 AEs (8.5% vs 21.4%) when compared to the 200 mg AE profile.

Overall, preliminary safety data from 199 participants in Study CA017003 reveal an overall safety profile of 100 mg BMS-986205 combined with nivolumab consistent with that observed with nivolumab monotherapy, including IMAEs such as pneumonitis (2%), autoimmune hepatitis (1%), colitis (1%), and uveitis (1%). The safety profiles differ with respect to AEs potentially associated with p-chloroaniline production during metabolism of BMS-986205, including anemia and methemoglobinemia. These events were reported infrequently in participants receiving the 100 mg dose (treatment-related anemia of any grade in 3.5% of participants and Grade 3 in 1% of participants receiving 100 mg; Grade 1 methemoglobinemia in 0.5% of participants).

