#### **7.4.2 BMS-986205 Dose Modifications**

A dose reduction of BMS-986205 is defined as a change from a 100 mg QD tablet to a 50 mg QD tablet.

Only one dose reduction is permitted. The participant must discontinue study treatment if a subsequent dose reduction of BMS-986205 is required (see [Section 8.1.2](#)).

Re-escalation of BMS-986205 will not be permitted once the dose of BMS-986205 has been reduced for a participant.

Doses of BMS-986205 should be reduced for the following AEs attributable to study therapy that do not otherwise meet criteria for discontinuation:

- Grade 3 fatigue, nausea, vomiting, or anemia related to study treatment
- Methemoglobin  $\geq 15\%$

- Clinically significant elevations in methemoglobin (generally 10%, with a normal hemoglobin level) with any associated Grade 3 AE (hypoxia, dyspnea, confusion, etc.) attributable to sustained elevations of methemoglobin and not attributable to another etiology
- QTcF > 500 msec confirmed by at least 1 repeat ECG and at least 60 msec above baseline (See [Appendix 8](#))

Dose modification and delay of BMS-986205 may occur in the setting of lower grade AEs and/or be more conservative than indicated above based on the clinical judgment of the investigator and in consultation with the BMS Medical Monitor/designee. For an AE requiring dose modification, BMS-986205 should be delayed to allow improvement of the AE, even if the AE does not otherwise meet criteria for dose delay (Section 7.4.4.2).

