#### **7.4.4.2 Nivolumab Plus BMS-986205**

Nivolumab and BMS-986205 administration should be delayed for the following:

- Grade 2 non-skin, drug-related AE, with the exception of fatigue, nausea, vomiting and anemia

- Grade 2 drug-related creatinine, AST, ALT and/or Total Bilirubin abnormalities
- Grade 3 skin, drug-related AE
- Grade 3 drug-related fatigue, nausea, vomiting, and anemia
- Grade 3 drug-related laboratory abnormality, with the following exceptions:
  - Grade 3 lymphopenia or asymptomatic amylase or lipase elevations do not require dose delay
  - Grade  $\geq 3$  AST, ALT, or Total Bilirubin will require dose discontinuation (see [Section 8.1](#))
- SARS-CoV-2 infection, either confirmed or suspected
- Any AE, laboratory abnormality, or intercurrent illness which, in the judgment of the investigator, warrants delaying the dose of study medication

If nivolumab dosing is delayed for reasons other than study drug toxicity (eg, administrative issues, holidays, etc.), BMS-986205 dosing should continue uninterrupted.

In addition, **only BMS-986205** should be delayed for the following:

- Methemoglobin  $\geq 15\%$
- Clinically significant elevations in methemoglobin (generally 10% with a normal hemoglobin level) with any associated Grade 3 AE (hypoxia, dyspnea, confusion, etc.) attributable to sustained elevations of methemoglobin and not attributable to another etiology
- QTcF  $> 500$  msec confirmed by at least 1 repeat ECG and at least 60 msec above baseline (See [Appendix 8](#))

Participants may continue to receive nivolumab during dose delays of BMS-986205 for elevations of methemoglobin and associated events, as well as QTcF prolongations.

For participants with methemoglobin elevations with associated Grade 3 AEs, if a contribution of nivolumab to the associated AE cannot be ruled out (eg, a participant with dyspnea in whom pneumonitis has not yet been ruled out), nivolumab dosing should be delayed as well. See [Section 7.7.4](#) for management of methemoglobinemia.

If BMS-986205 dosing is delayed, dose reduction may be necessary. See [Section 7.4.2](#).

If dosing is resumed after a delay, BMS-986205 may be resumed as soon as the criteria to resume treatment are met (see [Section 7.4.5.2](#)). Nivolumab should be resumed as soon as possible after criteria to resume treatment are met but may be resumed later than BMS-986205 given the differences in each drug's administration.

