**Table 7.4.4.2-1: Summary Table for Dose Delay and Reduction**

Situation	Nivolumab delay	BMS-986205 delay	BMS-986205 Reduction after Delay
Grade 2 non-skin, drug-related AE, except fatigue, nausea, vomiting and anemia	Yes	Yes	No
Grade 2 drug-related creatinine, AST, ALT and/or Total Bilirubin abnormalities	Yes	Yes	No
Grade 3 skin, drug-related AE	Yes	Yes	No
Grade 3 drug-related laboratory abnormality (exceptions apply)	Yes	Yes	No
Grade 3 drug-related fatigue, nausea, vomiting, and anemia	Yes	Yes	Yes
Methemoglobin $\geq$ 15% or any clinically significant elevation with associated Gr 3 AE not attributable to another etiology	No	Yes	Yes
QTcF > 500 msec (and > 60 msec above baseline)	No	Yes	Yes
Other lower grade AEs (in consultation with Medical Monitor/designee)	Possibly Yes	Possibly Yes	Possibly Yes

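### Section 7.1.1 continues BMS-986205 through any nivolumab delay, but Section 7.4.4.2 and its summary table hold both drugs for drug-related toxicity

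*Combined protocol and SAP*

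**What the plan says.** Section 7.1.1 (Nivolumab Dosing) introduces changes to nivolumab dosing as a matter of tolerability: "Doses of nivolumab may be interrupted (ie, infusion interruption), delayed, or discontinued depending on how well the participant tolerates the treatment". Two sentences later it states that "BMS-986205 treatment should be continued if nivolumab dosing is interrupted or delayed". The section does not refer to Section 7.4.4.2; its only pointer is to Section 7.7.5, for infusion reactions.

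Section 7.4.4.2 sets the delay rules for the combination: "Nivolumab and BMS-986205 administration should be delayed for the following". Seven events follow. Five are drug-related toxicities. The other two are confirmed or suspected SARS-CoV-2 infection and a judgment item: "Any AE, laboratory abnormality, or intercurrent illness which, in the judgment of the investigator, warrants delaying the dose of study medication". Table 7.4.4.2-1, which covers Arms C and D, repeats the five toxicities, beginning with "Grade 2 non-skin, drug-related AE, except fatigue, nausea, vomiting and anemia", and marks both drugs as delayed for each.

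Sections 7.1.2 and 7.4.4.2 each say that BMS-986205 carries on without a break when nivolumab is delayed for something other than study drug toxicity, with administrative issues and holidays as examples. Section 7.1.3 makes BCG delays independent of the other drugs but states a toxicity exception explicitly.

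**The concern.** Two operative dosing instructions give opposite answers to the same question: should a participant whose nivolumab is held for drug-related toxicity keep taking the daily BMS-986205 tablet? Section 7.1.1 says yes and Section 7.4.4.2 says no.

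The conflict concerns delays only. Continuing the tablet through an infusion interruption contradicts nothing.

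It is still live, because Section 3.1.2 (Amendment 04) lets participants already on treatment continue. The anemia case shows what is at stake. Section 5.5.2 says of the combination compared with nivolumab alone: "The safety profiles differ with respect to AEs potentially associated with p-chloroaniline production during metabolism of BMS-986205, including anemia and methemoglobinemia". For Grade 3 drug-related anemia, a site acting on Section 7.1.1 alone would go on giving the drug whose metabolite is under suspicion.

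**Working it through.** There is no plan figure to reproduce. The check is a row count of Table 7.4.4.2-1 and a comparison of the texts.

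**1. Row count of Table 7.4.4.2-1**

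| Situation (abbreviated) | Nivolumab delay | BMS-986205 delay | BMS-986205 reduction after delay |
|---|---|---|---|
| Grade 2 non-skin AE, with exceptions | Yes | Yes | No |
| Grade 2 creatinine, AST, ALT, bilirubin | Yes | Yes | No |
| Grade 3 skin AE | Yes | Yes | No |
| Grade 3 laboratory abnormality, with exceptions | Yes | Yes | No |
| Grade 3 fatigue, nausea, vomiting, anemia | Yes | Yes | Yes |
| Methemoglobin elevation | No | Yes | Yes |
| QTcF prolongation | No | Yes | Yes |
| Other lower-grade AEs | Possibly | Possibly | Possibly |

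- Both drugs delayed: 5 rows.
- BMS-986205 only: 2 rows.
- Possibly both: 1 row. Total 5 + 2 + 1 = 8.
- Nivolumab delayed and BMS-986205 continued, the pattern in Section 7.1.1: 0 rows.
- Of the 5 both-drug rows, 1 also requires a BMS-986205 reduction.

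**2. Events in the text of Section 7.4.4.2**

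5 drug-related toxicities + SARS-CoV-2 infection + the investigator-judgment item = 7 events that delay both drugs. Section 7.1.1, read literally, conflicts with all 7.

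**3. Does Amendment 04 settle it?**

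Section 3.1.2 gives the amendment's changes priority over existing requirements. The only change the amendment lists for Section 7.4.4.2 is the SARS-CoV-2 hold, so the override settles that item: 7 − 1 = 6 remain. The toxicity holds are not among the amendment's changes, and the override does not reach them.

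**4. Can Section 7.1.1 be read as meaning administrative delays only?**

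No. The paragraph is framed by tolerability ("Doses of nivolumab may be interrupted (ie, infusion interruption), delayed, or discontinued depending on how well the participant tolerates the treatment"), so toxicity delays are within its scope. Section 7.1.2 confines its own continuation sentence to delays for other reasons, and Section 7.1.3 writes out an exception. Section 7.1.1 does neither.

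**5. Grade 3 drug-related anemia, section by section**

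- Section 7.4.2: reduce BMS-986205, and first hold it: "For an AE requiring dose modification, BMS-986205 should be delayed to allow improvement of the AE".
- Section 7.4.4.2 and the table: delay both drugs, then reduce BMS-986205.
- Section 7.1.1: once nivolumab is delayed, continue BMS-986205.

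Section 3.3 puts drug-related Grade 3 anemia at about 1.4% in the first-in-human study. Section 5.5.2 gives 1% at the 100 mg dose.

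**6. Size in doses**

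The two readings differ by one tablet (100 mg, or 50 mg if already reduced) per day of hold. The documents do not fix the length of a hold. Participants are re-evaluated weekly or more often, and on restarting, nivolumab "may be resumed later than BMS-986205 given the differences in" how each is given. Total doses and people affected therefore cannot be calculated.

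**7. A smaller related gap**

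The sentences in Sections 7.1.2 and 7.4.4.2 about reasons other than study drug toxicity, taken literally, would also continue BMS-986205 during SARS-CoV-2 infection or an intercurrent illness unrelated to the drugs. Section 7.4.4.2 holds both drugs for the former, and for the latter when the investigator judges a delay warranted.

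**The case against.** The strongest reply is that the protocol states the right rule in several places and only one sentence is loose. The Synopsis sends delays of all three drugs for treatment-related AEs to Section 7.4. Section 7.1.2, which governs BMS-986205, says its doses may be delayed according to tolerability and cites Section 7.4.4.2. Section 7.1.1 contains no delay criteria, so a site deciding whether to delay must go to Section 7.4.4, where it meets the both-drug hold. Grade 3 anemia is covered three times over: in Section 7.4.2, in Section 7.4.4.2 and in its own table row.

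The count of 0 rows can also be discounted. The table lists adverse event situations, so administrative delays have no row, and the text of Sections 7.1.2 and 7.4.4.2 does allow BMS-986205 to continue through those. Counting the judgment item as a conflict is weak too, since the investigator is the one deciding the hold.

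Most of this stands as mitigation. It shows which rule was intended and makes harm less likely. The 0 of 8 count shows only that no listed toxicity follows the Section 7.1.1 pattern; it does not show that the pattern is never valid. None of it removes an unqualified instruction to continue an investigational drug in a paragraph about tolerability. The smaller gap in step 7 is a matter of tidying: the examples given there make the intended meaning fairly clear.

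**Conclusion.** The concern holds. As written, Section 7.1.1 contradicts Section 7.4.4.2 on 7 events, or 6 once the Amendment 04 override settles SARS-CoV-2. It contradicts all 5 table rows with a definite nivolumab delay. This is an internal inconsistency in an operative dosing rule, worth correcting for the safety of Arm C and D participants on treatment.

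The conclusion rests on reading delay in Section 7.1.1 to include tolerability delays, which its own paragraph supports. It does not assume that any site has followed the wrong rule. Enrollment is closed, the documents do not say how many Arm C or D participants remain on treatment, and no statistical quantity in the plan is affected.

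**What to change.** Replace the Section 7.1.1 sentence with wording to this effect:

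> When nivolumab is delayed for an event that Section 7.4.4.2 lists as delaying both drugs (drug-related toxicity, SARS-CoV-2 infection, or an AE, laboratory abnormality or illness for which the investigator judges delay necessary), delay BMS-986205 as well. Resume it under Section 7.4.5.2, with any reduction that Section 7.4.2 requires. For any other nivolumab delay, or an infusion interruption alone, continue BMS-986205 unless Section 7.4.4.2 separately requires it to be held.

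Optionally, in Sections 7.1.2 and 7.4.4.2, limit the continuation sentence to delays for reasons that Section 7.4.4.2 does not list as delaying both drugs. This closes the smaller gap.

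The cost is one sentence, or three with the optional edits, in a clarification letter to sites or the next amendment. It needs no new data, visits or participants.
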